3.11.2 Statistical methods for Biomarker

Mutations involved in the molecular disease characterization of MF will be listed by patient and summarized using frequency tables by study treatment.

The expression levels of Hh pathway related biomarkers (such as Gli1) and JAK signaling pathway related biomarkers (such as JAK2V617F allele burden; reported as percent mutated) and cytokine levels will be reported and summarized as follows:

All data will be listed by patient in each cohort and time point. Summary tables of the expression levels will be created at each measured time point by study treatment in Phase Ib and Phase II Stage 1. Summary tables will include number of samples (n), % of those samples below LLOQ, mean, standard deviation, median, %CV, minimum and maximum. For all post-baseline time-points; fold change in biomarker expression levels will also be summarized. The summary statistics will include, number of samples, mean, geometric mean, %CV of geometric mean, minimum, maximum etc. Additionally frequency tables (number and percentage of subjects) for JAK2 mutation status (positive/negative) at baseline will be reported.

Longitudinal plots of the mean fold-change from baseline along with 95% CI's or standard error bars will be created to explore the trend over time.

The associations between biomarkers and efficacy outcomes may also be explored via more sophisticated statistical models if sufficient data are available. Advanced statistical analysis may be carried out to explore the data in a post-hoc fashion. Details of such methodology if applied to the data will be described in a separate Biomarker Analysis Plan document.

3.12 Pharmacokinetic analyses

The pharmacokinetic analyses will be based on the PAS described in [section 2.2.4](#), unless otherwise specified.

Listings will be presented by study treatment using FAS and ordered according to instructions detailed in the general guidance section of RAP M7.

As convention, a PK sample should be excluded from analyses if the patient vomited within the first 4 hours following the last oral dose of study drug. Other PK samples will be excluded as deemed appropriate by the Pharmacokineticist. The excluded concentrations will be flagged in the listings.

All concentrations below the limit of quantification or missing data will be labeled as such in the concentration data listings. Concentrations below the limit of quantification will be treated as zero in summary statistics and for the calculation of pharmacokinetic parameters.

3.12.1 Trough and profile concentration data

Plasma concentrations of LDE225 and INC424 will be summarized at each scheduled time point by study phase and dose cohort. Profile concentration data for LDE225 refers to the data collected on week 1 day 1 (also include pre-dose and week 1 day2) and week 9 day 1 (also include pre-dose and week 9 day 2). Profile concentration data for INC424 refers to the data collected on week 1 day 1 within the 12 hours after the first dose and before the second dose, and week 9 day 1 within the 12 hours after the first dose and before the second dose. Trough concentration data refers to pre-dose samples eg week 3 day1, week 5 day 1, week 7 day1, week 13 day1, etc. Descriptive graphical plots of individual plasma concentration time profiles with median will be generated, along with geometric mean and mean (SD) concentrations time profiles trough concentrations for LDE225 and INC424. Individual plots of trough concentrations for LDE225 and INC424 will also be produced. A list of individual concentrations will be provided using FAS. Concentrations excluded from analyses will be flagged. Descriptive statistics will include n (number of patients), m (number of non-zero concentrations), arithmetic mean, geometric mean, median, SD, coefficient of variation CV (%), geometric CV (%), minimum and maximum.

Coefficient of variation CV (%) is calculated as follows: $100 \times (\text{SD} / \text{arithmetic mean})$.

Geometric CV (%) is calculated as follows: $100 \times \sqrt{\exp[\text{Var}(\log(x))] - 1}$, where $\text{Var}(X)$ denotes the variance of X.

3.12.2 Pharmacokinetic parameters

For Phase Ib and Phase II Stage 1 only, PK parameters listed in [Table 3-6](#) and [Table 3-7](#) will be determined for all PK-evaluable patients using non-compartmental method(s) using WinNonlin or Phoenix WinNonlin (Pharsight, Mountain View, CA). PK parameters will be estimated for Week 1 and Week 9 and reported, when feasible. PK parameters in [Table 3-6](#) and [Table 3-7](#) for LDE225 and INC424 will be descriptively summarized for Week 1 and Week 9 by dose level.

Descriptive statistics (n, mean, SD, CV% or median [range], and geometric mean and CV%) will be presented for all parameters with the exception of T_{max} for which median values and ranges will be presented. When a geometric mean is presented, it will be stated as such.

The following pharmacokinetic parameters are determined using non-compartmental method(s) ([Table 3-6](#) and [Table 3-7](#)).

Table 3-5 Non-compartmental pharmacokinetic parameters for LDE225 (Phase Ib and Phase II Stage 1 only)

Term	Definition
C _{max}	Maximum observed plasma concentration after drug administration [mass x volume ⁻¹]
T _{max}	Time to reach C _{max} [time]
AUC _{0-24h}	Area under the concentration-time curve from time zero to 24 hours [mass x time x volume ⁻¹]
CL/F	Apparent total plasma clearance of drug after oral administration [volume x time ⁻¹]

Term	Definition
Racc	Accumulation ratio calculated as AUC0-24h on Week 9 Day 1 divided by AUC0-24h on Week 1 Day1 [fold]

Table 3-6 Non-compartmental pharmacokinetic parameters for INC424 (Phase Ib and Phase II Stage 1 only)

Term	Definition
Cmax	Maximum observed plasma concentration after drug administration [mass x volume ⁻¹]
Tmax	Time to reach Cmax [time]
AUClast	Area under the concentration-time curve from time zero to the time of last measurable concentration [mass x time x volume ⁻¹]
AUC0-12h	Area under the concentration-time curve from time zero to 12 hours extrapolate from AUClast [mass x time x volume ⁻¹]
AUCinf	Area under the concentration-time curve from time zero to infinity with extrapolation of the terminal phase [mass x time x volume ⁻¹]
T1/2	Elimination half-life associated with the terminal slope (λ_z) of a semi logarithmic concentration-time curve [time]
CL/F	Apparent total plasma clearance of drug after oral administration [volume x time ⁻¹]
Racc	Accumulation ratio calculated as AUC0-12h on Week 9 Day 1 divided by AUC0-12h on Week 1 Day 1 [fold]
Vss/F	Apparent volume of distribution at steady state after oral administration [volume]

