The major changes included in this amendment include: Addition of an exploratory endpoint to assess the levels of LDE225 in bone marrow, updates to the guidance for contraception based on a recent population pharmacokinetic analysis and updates to the muscle toxicity section for CK elevation.

[figure not shown]
Changes to contraception language

The recommendation for contraception duration has been updated based on a recent population pharmacokinetic analysis that showed a longer half-life of sonidegib in cancer patients (28 days) than in healthy subjects (10 days). Duration of pregnancy prevention was estimated via population pharmacokinetic model-based simulations incorporating the emerging data in cancer patients. The recommended duration of pregnancy prevention in female patients was extended from 6 months to 20 months to ensure the residual plasma sonidegib concentration is reduced below the safety threshold of 3pg/mL. The recommended condom use for 6 months for male patients with partners of child-bearing potential did not change as the 6-month duration is considered adequate to minimize any risk of sonidegib being transmitted to female partners via the seminal fluid of male patients. Female patients of child-bearing potential who had discontinued sonidegib before the current protocol amendment were informed of the need for extended contraception for 20 months.

Changes to the protocol:

The following sections have been changed in the amended protocol:

Changes to the title page:

- The LDE225 International Nonproprietary Name (INN), sonidegib, added.
- Author list updated.

List of abbreviations updated.

Glossary of terms updated.

Protocol summary (Purpose and rationale): Updated number of countries INC424 is approved in.

Protocol summary (Exclusion criteria): revised aspirin dose to 150mg/day to be consistent with other INC424 studies.

Protocol summary (Other assessments): Inserted ‘Bone marrow aspirate samples for pharmacokinetic and pharmacodynamic analysis.

Section 1.4.1.2.1: Updated the total number of subjects, including patients that were dosed with LDE225 as of the most recent Investigator Brochure.

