Section 1.4.1.2.3: Updated information from a food effect study. ‘In study [CLDE225A2114] in healthy volunteers with a 12-week follow-up period after a single dose, the geometric mean terminal half-life is estimated to be 10 days with a range of 3-32 days. In addition, a high-fat meal increased the C_{max} and AUC of LDE225 capsules compared with the fasting condition. In anticipation of a food effect, food consumption will continue to be restricted around the time of dosing in clinical studies.’

Section 1.4.1.2.3 – Inserted language based on an update from a recent population pharmacokinetic analysis.

Section 1.4.2: Updated number of countries INC424 is approved in.

Section 1.4.2.2: Updated the total number of subjects and patients that were dosed with INC424 as of the most recent Investigator Brochure.

Section 1.4.2.2.1: Updated data for tuberculosis reports.

Section 1.4.2.2.1: Added PML (Progressive Multifocal Leukoencephalopathy) language.

Section 3: Table 3-1, added a new Phase II exploratory objective ‘To assess the levels of LDE225 in bone marrow’

Section 4.1: Figure 4-1, Clarified in the study schema that the Phase Ib part of the study is comprised of an escalation and safety expansion stage. Also included mention of the roll-over study.

Section 4.1.1: Added bone marrow aspirate sample collection for LDE225 concentration measurement.

Section 4.1.2: Updated section to be consistent with the LDE225 program roll-over study language.

Section 5.1: Sentence updated to indicate that only JAK inhibitor naïve patients are allowed into the study to be consistent with the rest of the document.

Section 5.3: Exclusion criteria #7, revised allowable aspirin dose level to 150mg/day to be consistent with other INC424 studies.

Section 5.3: Exclusion criteria #16: The time period for which women of child-bearing potential must use highly effective contraception after the final dose of study treatment was increased from 6 to 20 months.

Section 5.3: Exclusion criteria #16: Clarified that male patients should use contraception and refrain from fathering a child for 6 months following the last dose of study drug.

Section 6.2.5: Table 6-3, updated the toxicity classification for liver function DLTs to “Hepatic”.

[REDACTED]

Section 6.4.3.4: Reworded this section for greater clarity.

Section 6.5.1: Removed reference to patient numbering in the setting of re-screening since re-screening is not allowed in the study.

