6.6 Study drug supply

6.6.1 Study drug preparation and dispensation

Study medication will be dispensed by an authorized person at the investigator's site. Patients will be provided with an adequate supply of study drug for self-administration at home, including instructions for administration, until at least their next scheduled study visit. Patients will receive LDE225 and INC424 study treatment on an outpatient basis. The investigator shall provide the patient with instructions for study treatment administration according to the protocol.

All dosages prescribed to the patient and all dose changes and/or missed doses during the study must be recorded on the Dosage Administration Record eCRF.

When possible, individual doses will consist of the minimum number of capsules/tablets equaling the total dose given the available capsule/tablet sizes.

[figure not shown]

Table 6-8 Preparation and dispensing

| Study treatments | Dispensing | Preparation |
|------------------|-----------------------------|----------------|
| LDE225 | Continuous daily QD dosing | Not applicable |
| INC424 | Continuous daily BID dosing | Not applicable |

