7.2.3 Pharmacokinetics

Blood collection

The blood sampling schedule for determining the PK of LDE225 and INC424 are provided in [Table 7-7](#) (for Phase Ib and Phase II, Stage 1) and [Table 7-9](#) (for Phase II, Stage 2). Blood samples for PK determinations will not be obtained during the extension phase of the study. The 24 hours plasma concentration-time profiles of LDE225 and INC424 will be characterized after single dose (Week 1 Day 1) and after multiple doses (Week 9 Day 1) in Phase Ib and Phase II Stage 1. Trough (pre-dose) samples will be collected on Week 3 Day 1, Week 5 Day 1, Week 7 Day 1, Week 9 Day 1 and Day 1 of every 4 weeks thereafter until Week 49. Only trough samples will be collected in Phase II, Stage 2. On the day of trough samples, the doses of LDE225 and INC424 should be taken at the clinic after pre-dose collection. At each scheduled time point, a single blood draw (4mL) will be collected into tubes containing K2EDTA, and the plasma will be split into 2 tubes (approximately 1 mL for LDE225 and approximately 1 mL for INC424 concentration measurement). Complete instructions for sample processing, handling and shipment will be provided in the [\[Laboratory Manual\]](#).

If a patient experiences an adverse event that results in an unscheduled visit or fits the criteria of an SAE as determined by the Investigator, a blood sample should be collected for measurement of plasma drug concentrations.

Exact dates and clock times of drug administration and actual PK blood draw will be recorded on the appropriate eCRF. If vomiting occurs within 4 hours of dosing during the course of treatment, no re-dosing of the patient is allowed before the next scheduled dose. The time of vomiting should be recorded on the appropriate eCRF.

Meal records will be collected on Week 1 Day 1 and Week 9 Day 1 for Phase Ib and Phase II Stage 1 only. The start and end time of meals will be recorded.

Table 7-7 Pharmacokinetic blood collection log: Phase Ib and Phase II, Stage 1

[figure not shown]
| Week/Day | LDE225 | | | INC424 | | |
|--------------|--------------|-------------------|------------|--------------|-------------------|------------|
| | Time (hours) | Dose reference ID | Sample No. | Time (hours) | Dose reference ID | Sample No. |
| Week 1 day 1 | Pre-dose | 101 | 101 | Pre-dose | 201 | 201 |
| | 0.5 | 101 | 102 | 0.5 | 201 | 202 |
| | 1 | 101 | 103 | 1 | 201 | 203 |
| | 1.5 | 101 | 104 | 1.5 | 201 | 204 |
| | 2 | 101 | 105 | 2 | 201 | 205 |

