10.5.2 Pharmacokinetics

Plasma concentrations of LDE225 and INC424 will be summarized at each scheduled time point by dose level. Descriptive graphical plots of individual plasma concentrations over time will be generated, along with mean concentration time profiles and trough for LDE225 and INC424. A list of individual concentrations will be provided using FAS.

For Phase Ib and Phase II Stage 1 only, PK parameters listed in [Table 10-3](#) and [Table 10-4](#) will be determined for all PK-evaluable patients using non-compartmental method(s) using WinNonlin or Phoenix WinNonlin (Pharsight, Mountain View, CA). PK parameters will be estimated for Week 1 and Week 9 and reported, when feasible. PK parameters in [Table 10-3](#) and [Table 10-4](#) for LDE225 and INC424 will be descriptively summarized for Week 1 and Week 9 by dose level. For Phase II Stage 2, Ctrough will be descriptively summarized at each scheduled time point and by means of graphical display.

Descriptive statistics (n, mean, SD, CV%, median [range], and geometric mean and CV%) will be presented for all parameters with the exception of Tmax for which median values and ranges will be presented. When a geometric mean is presented, it will be stated as such.

[figure not shown]

Table 10-3 Noncompartmental pharmacokinetic parameters for LDE225 (Phase Ib and Phase II Stage 1 only)

| Term | Definition |
|----------------------|--|
| C _{max} | Maximum observed plasma concentration after drug administration [mass x volume ⁻¹] |
| T _{max} | Time to reach C _{max} [time] |
| AUC _{0-24h} | Area under the concentration-time curve from time zero to 24 hours [mass x time x volume ⁻¹] |

Table 10-4 Noncompartmental pharmacokinetic parameters for INC424 (Phase Ib and Phase II Stage 1 only)

| Term | Definition |
|----------------------|---|
| C _{max} | Maximum observed plasma concentration after drug administration [mass x volume ⁻¹] |
| T _{max} | Time to reach C _{max} [time] |
| AUC _{last} | Area under the concentration-time curve from time zero to the time of last measurable concentration [mass x time x volume ⁻¹] |
| AUC _{0-12h} | Area under the concentration-time curve from time zero to 12 hours extrapolate from AUC _{last} [mass x time x volume ⁻¹] |
| AUC _{inf} | Area under the concentration-time curve from time zero to infinity with extrapolation of the terminal phase [mass x time x volume ⁻¹] |

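### The SAP adds CL/F for LDE225: it cannot be estimated at Week 1, and at Week 9 Dose/AUC0-24h would overstate it, by up to about 32% under a one-compartment model with a 28-day half-life

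*SAP*

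**What the plan says.** **Protocol, section 10.5.2.** Table 10-3, headed "Noncompartmental pharmacokinetic parameters for LDE225 (Phase Ib and Phase II Stage 1 only"), contains Cmax, Tmax and AUC0-24h. CL/F, AUCinf and T1/2 appear only in Table 10-4, for INC424, whose half-life is about 3 hours (protocol 1.4.2.2.2).

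**SAP, section 3.12.2.** The LDE225 table (captioned Table 3-5, though the text calls it Table 3-6) keeps those three parameters and adds CL/F and Racc. Racc is AUC0-24h at Week 9 over AUC0-24h at Week 1. CL/F is described as "Apparent total plasma clearance of drug after oral administration", with no formula and no statement of which AUC or which week it uses. The table has no AUCinf and no T1/2. Parameters are to be estimated at Week 1 and Week 9, where that is feasible, and summarised by dose level.

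**Sampling.** Dosing is "Continuous daily QD dosing" (protocol Table 6-8). The 24-hour profiles "will be characterized after single dose (Week 1 Day 1) and after multiple doses (Week 9 Day 1") (protocol 7.2.3). Protocol Table 7-7 places samples up to 8 hours and then at the next morning's pre-dose time; SAP 3.12.1 defines the LDE225 profile in the same way.

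**Half-life.** The Amendment 1 rationale reports a "longer half-life of sonidegib in cancer patients (28 days) than in healthy subjects (10 days"). The Amendment 1 list of changes says of healthy volunteers that "the geometric mean terminal half-life is estimated to be 10 days with a range of 3-32 days".

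**The concern.** Non-compartmental CL/F needs one of two quantities: AUC to infinity after a single dose, or AUC over a dosing interval at steady state. With a half-life of weeks, a 24-hour first-dose profile cannot give the first. With a 28-day half-life, Week 9 does not give the second.

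The two weeks carry different risks. A Week 1 value would look absurd and would probably be dropped. A Week 9 value, Dose/AUC0-24h, can be calculated for any patient with a complete profile and will look reasonable. Nothing in either document warns that Week 9 may be short of steady state, so the figure could be reported as the drug's clearance when it is too high. PK characterisation is a secondary objective in both phases, so the table will be read.

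**Working it through.** The documents give no CL/F value, bias or steady-state fraction for LDE225, so there is no plan figure to reproduce. What follows is linear superposition.

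**Inputs**
- Dosing interval: 24 hours (protocol Table 6-8).
- Doses by Week 9 Day 1: 8 × 7 + 1 = 57, if none is missed. The visit window is ±2 days (protocol 7.1), so 55 to 59.
- Half-life (t½): 28 days in cancer patients and 10 days in healthy subjects (Amendment 1 rationale). The healthy-volunteer range is 3 to 32 days.
- Assumptions: CL/F is taken as Dose/AUC0-24h, and kinetics are linear and one-compartment.

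**Week 1.** Share of AUCinf in the first 24 hours = 1 − 2^(−1/t½).
- 28 days: 1 − 2^(−1/28) = 0.0245, about 2.4%. Dose/AUC0-24h would be 1/0.0245, about 41 times the true CL/F. The profile spans 1/28 = 0.036 of a half-life, so the terminal slope cannot be estimated either.
- 10 days: 1 − 2^(−1/10) = 0.067. Dose/AUC0-24h would be about 15 times too high.

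**Week 9.** Fraction of steady-state AUC after dose n = 1 − 2^(−n/t½). Overstatement of CL/F = 1/fraction − 1.

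| Half-life (days) | Fraction at n = 57 | Overstatement |
|---|---|---|
| 10 | 0.981 | 2.0% |
| 20 | 0.861 | 16.1% |
| 28 | 0.756 | 32.3% |
| 32 | 0.709 | 41.0% |

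At 28 days the visit window moves the result from 34.5% (n = 55) to 30.2% (n = 59). Numerical superposition with first-order absorption (assumed ka of 0.5 and 1.0 per hour) also gives 32.3%. Reaching 90% of steady state would take about 93 days of dosing, and 95% about 121 days.

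**Faster distribution phase.** Suppose that only a share w of the AUC belongs to the 28-day phase and the rest is complete by day 57. The fraction is then 1 − w × 2^(−57/28) = 1 − 0.244w. The values of w are assumptions.

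| w | Overstatement |
|---|---|
| 1.00 | 32.3% |
| 0.90 | 28.1% |
| 0.75 | 22.4% |
| 0.50 | 13.9% |
| 0.25 | 6.5% |

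**Racc.** In the absorption model at 28 days, the Week 9/Week 1 ratio is about 32 to 34, against about 43 to 45 at steady state. It is a valid ratio of two observed AUCs, but not the steady-state accumulation ratio.

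**The case against.** Four points deserve weight.

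1. *The size is conditional.* The SAP gives no CL/F formula, and the text available for this review shows no compartment structure for LDE225. The protocol's clinical PK section 1.4.1.2.3, which the amendment log says received the population PK update, was not in that text. A reader might conclude that Week 9 CL/F will be 32% too high; the documents do not support a flat figure. This objection stands. It limits the size, not the direction, which is upward whenever Week 9 is short of steady state on constant dosing.

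2. *The feasibility qualifier.* It allows the analyst to leave Week 1 unreported, and without AUCinf in the table nothing forces a Week 1 CL/F. This largely holds for Week 1. It does not help at Week 9, where the calculation is always feasible.

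3. *Consequences.* A reader might infer that the bias would distort comparisons between dose levels or with monotherapy. The plan describes no monotherapy comparison of CL/F. Under the same linear model with a common half-life, the proportional bias is equal at every dose. The exposure plots in SAP 3.12.3 use AUC and Cmax. This objection stands.

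4. *Agreement with the protocol.* Deleting CL/F might seem to bring the SAP into line with protocol Table 10-3. It would not, because Racc is also an addition.

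**Conclusion.** The point holds as a minor one. CL/F for LDE225 is an SAP addition that the sampling cannot support. At Week 1 it is not estimable at either documented central half-life. At Week 9, Dose/AUC0-24h is biased upward.

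About 32% is the upper value for a 28-day half-life. It rests on four conditions: CL/F computed as Dose/AUC0-24h, one-compartment linear kinetics, all accumulation governed by the 28-day half-life, and 57 doses with none missed. If part of the AUC lies in a faster phase the bias is smaller, and at the healthy-subject half-life it almost vanishes. It is not a ceiling for individual patients, since a half-life of 32 days would give 41%.

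The effect stays within a descriptive secondary PK table. Dose meetings weigh PK in general terms, but no dose, efficacy or go/no-go rule uses CL/F, and the primary endpoint is untouched.

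**What to change.** Choose one of these for the LDE225 table in SAP 3.12.2:

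- Delete the CL/F row. Dose and AUC0-24h are still reported, so no data are lost.
- Keep it for Week 9 only, define it as Dose/AUC0-24h on Week 9 Day 1, and add a footnote that it is an apparent value not at steady state and is expected to overstate CL/F.

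In either case, add the same not-at-steady-state note to Racc and say that CL/F (if kept) and Racc are additions to protocol Table 10-3.

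The cost is one row or two footnotes, with no new sampling. If a proper clearance estimate is wanted, a population PK model is the natural source, but the documents reviewed commit to no such analysis of this study's data, so it would have to be planned separately.

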1.4.2.2.2 Human pharmacokinetic and metabolism data

INC424 exhibits near-complete absorption with maximal plasma concentration (C_{max}) achieved approximately 1 hour after a single oral dose. Linearity in PK was demonstrated over a dose range of 5 to 200 mg following single-dose administration. PK parameters were similar between single and multiple doses. A drug accumulation ratio of 1.12 was observed following twice daily dosing. The effect of food on the INC424 exposure (4% increase in AUC, 90% confidence interval, CI 96.8 – 113%) is not expected to be clinically significant.

INC424 may be administered without regard to meals. INC424 is eliminated almost completely by oxidative metabolism with a terminal elimination half-life of approximately 3 h. INC424 is excreted in urine and feces with less than 1% excreted as unchanged parent drug.

In vitro metabolism studies showed that CYP3A4 was the predominant human CYP isozyme responsible for the metabolism of INC424 with minor contribution from CYP2C9. Systemic co-administration of oral ketoconazole, a potent CYP3A4 inhibitor, resulted in a 91% increase of plasma AUC, whereas erythromycin, a moderate CYP3A4 inhibitor, caused a 27% increase in exposure. Based on these results, the dose of INC424 should be decreased by approximately 50% when a potent CYP3A4 inhibitor is concomitantly used and no dose adjustment is necessary when a mild or moderate CYP3A4 inhibitor is used. INC424 is not known to induce or inhibit other CYP enzymes.

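### The INC424 PK table lists a Vss/F that oral-only data cannot supply and does not limit AUCinf to Week 1, so the Week 9 value includes carry-over

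*SAP*

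**What the plan says.** SAP 3.12.2 gives one list of non-compartmental parameters for INC424 and applies it to two visits: "PK parameters will be estimated for Week 1 and Week 9 and reported, when feasible". It then says that the listed parameters will be summarised descriptively at Week 1 and Week 9 by dose level. Four entries matter here:

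- AUCinf: "Area under the concentration-time curve from time zero to infinity with extrapolation of the terminal phase".
- AUC0-12h: "Area under the concentration-time curve from time zero to 12 hours extrapolate from AUClast".
- CL/F: "Apparent total plasma clearance of drug after oral administration", with no formula.
- Vss/F: "Apparent volume of distribution at steady state after oral administration", with no formula and no mention of a correction for absorption time.

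No entry is restricted to one visit. Protocol 10.5.2 and Table 10-4 carry the same four entries and the same two visits. SAP 3.12.1 defines the second INC424 profile as "week 9 day 1 within the 12 hours after the first dose and before the second dose", that is, one dosing interval after eight weeks of twice-daily treatment. The accumulation ratio is the only derived quantity with an explicit basis: "Accumulation ratio calculated as AUC0-12h on Week 9 Day 1 divided by AUC0-12h on Week 1 Day 1".

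**The concern.** Two entries do not measure what their labels say when the text is followed as written.

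**Volume.** Non-compartmental Vss is clearance times the mean residence time of drug in the body. After an oral dose, the observed mean residence time is the disposition time plus the mean absorption time. Without intravenous data the two cannot be separated, and this trial has none.

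**Week 9 AUCinf.** On the first day, AUCinf is the exposure from one dose. At steady state, the curve from time zero to infinity also contains drug left from earlier doses. The one-dose equivalent at steady state is the AUC over the 12 h interval.

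Pharmacokinetics is a secondary objective in both phases. Protocol 2.3 states that LDE225 is not expected to affect INC424 kinetics, and a reader is likely to set the Week 1 and Week 9 columns side by side with that in mind. An artefact that raises AUCinf between those columns points toward apparent inhibition.

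**Working it through.** **Inputs.** Protocol 1.4.2.2.2 gives a half-life of about 3 h, a time to peak of about 1 h, linear single-dose kinetics, and "A drug accumulation ratio of 1.12 was observed following twice daily dosing". The dosing interval is 12 h. Not in the documents, and therefore assumed: one compartment with first-order absorption, linearity on repeat dosing, and the ranges of half-life and Tmax explored around the stated values.

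**1. The protocol's accumulation ratio.** Racc = 1/(1 - exp(-k x 12)).
- Half-life 3 h: k = ln2/3 = 0.231/h, exp(-12k) = 0.0625, Racc = 1/0.9375 = 1.07.
- Working back from 1.12: exp(-12k) = 1 - 1/1.12 = 0.107, k = 0.186/h, half-life about 3.7 h.

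This is compatible with a half-life of approximately 3 h. The protocol does not say whether 1.12 is an AUC or a Cmax ratio, so both half-lives are carried forward.

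**2. Vss/F at Week 1.** Solve ln(ka/k)/(ka - k) = Tmax for ka. Mean absorption time is 1/ka and disposition MRT is 1/k = 4.33 h. The ratio of CL/F x MRT to the true value is 1 + (1/ka)/(1/k).

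| Tmax (h) | 1/ka (h) | Ratio to true |
|---|---|---|
| 0.5 | 0.141 | 1.03 |
| 1 | 0.373 | 1.09 |
| 1.5 | 0.685 | 1.16 |
| 2 | 1.082 | 1.25 |

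**3. AUCinf at Week 9.** Under linear kinetics, steady-state AUC0-12h equals single-dose AUCinf. Week 9 AUCinf adds the tail beyond 12 h to that, so it must be larger; this direction needs no compartmental model. In the assumed model the excess is [ka/(ka - k)] x exp(-12k)/(1 - exp(-12k)).
- Half-life 3 h, Tmax 1 h (ka = 2.68/h): 1.094 x 0.0625/0.9375 = 0.073, about 7%.
- Half-life 3.7 h, Tmax 1 h: about 13%. Ignoring absorption time, the excess is Racc - 1 = 12%.

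**4. CL/F at Week 9, if computed as dose/AUCinf.** Ratio to true = 1/1.073 = 0.93 at 3 h, a fall of 6.8%. At the 1.12 ratio, 1 - 1/1.12 = 10.7%; with absorption included at 3.7 h the ratio is 0.89. Half-lives of 2.5 h and 5 h give falls of 4% and 20%. With dose/AUC0-12h the ratio is 1.00.

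**5. Vss/F at Week 9.** Two routes are open under the current text.
- AUMCinf/AUCinf times dose/AUCinf, all from the Week 9 profile: the low clearance offsets the long residence time. Ratios to true are 1.01 (3 h), 0.94 (3.7 h) and 0.83 (5 h).
- Dose/AUC0-12h with a steady-state MRT: 1.09 (3 h) and 1.06 (3.7 h).

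One row of the table could therefore carry a different bias at each visit.

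**6. The replacement.** Vz/F = (CL/F)/lambda_z contains no absorption-time term; in this model its ratio to true is 1.00 when CL/F is computed as in the fix.

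**The case against.** The strongest reply is that the clearance problem needs a formula the documents do not contain. That is correct. CL/F is undefined, AUC0-12h is in the same table, and an analyst could use the right one at Week 9. A reader might infer that the plan commits to a biased Week 9 clearance, or that the trial will report false inhibition by LDE225. The documents do not support either: no within-patient interaction test or criterion is planned, and Racc already rests on AUC0-12h.

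A reader might also infer that volume is overstated throughout. Step 5 shows that this holds at Week 1 but not reliably at Week 9. Nor is AUCinf invalid in general, since its first-dose use is sound.

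The sizes are modest and depend on the model, and no stated analysis, dose decision or endpoint uses Vss/F or CL/F. All of this stands, and it limits the weight of the point.

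The qualifier on feasibility in SAP 3.12.2 does not remove the point. It allows a parameter to be dropped when a profile cannot support it. Week 9 AUCinf and CL/F x MRT can both be computed; the difficulty is that they are not the quantities named.

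**Conclusion.** The point holds as a correction to descriptive secondary PK outputs. Vss/F is a wrong entry for oral-only non-compartmental data, overstated at Week 1 by about 9% (about 3% to 25% across Tmax of 0.5 to 2 h) and of uncertain direction at Week 9. AUCinf is a wrong entry at Week 9, where it runs about 7% to 13% above the single-dose value with no true change. The fall in CL/F of about 7% to 11% is conditional on dose/AUCinf being used at Week 9.

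That Week 9 AUCinf exceeds the single-dose value, and that oral MRT includes absorption time, follow from linear kinetics and oral dosing. The percentages rest on the one-compartment assumption and on the protocol's approximate half-life, Tmax and accumulation ratio. No primary result or decision rule is affected.

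**What to change.** In the INC424 table of SAP 3.12.2:

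- Replace Vss/F with Vz/F = (CL/F)/lambda_z.
- Report AUCinf at Week 1 only.
- Define CL/F as dose/AUCinf at Week 1 and dose/AUC0-12h at Week 9.

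It would also help to name the AUC and the visit used in the exposure-response box plots of SAP 3.12.3.1, which currently specify neither.

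The samples and software are unchanged; the cost is a few lines of SAP text. Protocol Table 10-4 should be aligned at the next amendment, since changing it needs the approvals in protocol 12.1 and does not justify an amendment of its own. The drawbacks are that a listed volume term is replaced by a different one (terminal-phase rather than steady-state volume), and that the SAP departs from the protocol table until that amendment, which the SAP should say.
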